5.3. Demographics and Baseline Disease Characteristics

Participant demographic data including age, age categories in years (e.g., <=40, >40), gender, race, ethnicity, height, weight, weight categories in kilograms (e.g., <=40, >40), BMI will be summarized descriptive summary statistics by cohort and overall in Safety Analysis Set.

The following baseline disease characteristics will be summarized using descriptive summary statistics by cohort and overall, for Safety Analysis Set: [REDACTED]

[REDACTED], time

since MS diagnosis, time since MS onset, number of prior DMTs and [REDACTED] in previous 12 months.

Medical history will be summarized using system organ class and preferred term by cohort and overall, in the Safety Analysis Set.

Demographics, baseline disease characteristics and medical history data will be presented in listings.

5.4. Protocol Deviations

Participants with major protocol deviations categorized according to Protocol Deviations Management Plan (PDMP) will be summarized by cohort and overall in Safety Analysis Set, using counts and percentage. All protocol deviations will be presented in a data listing.

5.7. Safety Endpoints

5.7.1. General Considerations

All safety analysis will be carried out using the Safety Analysis Set and will be summarized by each cohort and overall.

5.7.2. Adverse Events

An overview table, including number of participants with any TEAEs, TEAEs by severity, study treatment-related TEAEs, SAEs, study treatment-related SAEs, TEAEs

leading to drug interruption or dose reduction, TEAEs leading to study withdrawal or study treatment discontinuation will be provided by cohort and overall. SAEs leading to death will be summarized in the same table.

The incidence of TEAEs will be summarized for each cohort and overall, as follows:

- TEAEs by system organ class and preferred term (sorted by decreasing frequency and alphabetical order)
- TEAEs by system organ class
- TEAEs by preferred term
- TEAEs experienced by $\geq 5\%$ of participants by preferred term
- TEAEs by 4-week intervals by preferred term
- TEAEs of Special Interest by System Organ Class and Preferred Term
- Severe TEAEs by system organ class and preferred term
- Severe TEAEs by preferred term
- TEAEs by maximum severity by system organ class and preferred term
- TEAEs by maximum severity by preferred term
- Related TEAEs by system organ class and preferred term
- TEAEs that led to discontinuation of study treatment by system organ class and preferred term
- TEAEs that led to withdrawal from study by system organ class and preferred term
- TEAEs that led to drug dose reductions or interruptions by system organ class and preferred term
- TESAEs by system organ class and preferred term
- TESAEs by preferred term
- Related TESAEs by system organ class and preferred term

All AEs will be included in the participant-level listings. Supporting listings of SAEs, AEs leading to study treatment discontinuation, AEs leading to withdrawal from study, and AEs leading to death will be provided.

If more than one event occurred with the same preferred term for the same participant, the participant will be counted only once for that preferred term using the most severe occurrence for the summary table by severity. Similarly, if a participant has the same AE on multiple occasions, the closest relationship to study drug recorded for the event will be presented in the summary table for related events.

5.7.3. Adverse Events of Special Interest

Anaphylaxis and angioedema (serious events), PML (all events), Pancreatitis (all events), Serious and Opportunistic infections (serious events), Infections (serious), Lymphopenia and leucopenia (serious events), Liver injury (serious events and events leading to

treatment discontinuation), Pre-malignant conditions (all events), Malignancies (all events), Renal tubular injury (serious events), GI disorder (serious events or events leading to treatment discontinuation), Flushing and related events (serious events) and Cardiac disorders (all events).

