3.3. Benefit-Risk Assessment

The potential risks related to participation in this study are justified by the anticipated benefit to participants.

Detailed information about the known and expected benefits and risks and reasonably expected AEs of DRF is provided in the Investigator's Brochure and ICF. A high-level summary of those benefits and risks known during study design is provided here.

The safety profile of DRF relies on the well-known safety profile of the reference drug, DMF.

The safety of DMF has been established in 2 randomized, placebo-controlled, double-blind, pivotal Phase 3 studies (Study 109MS301 and Study 109MS302) and further established in extensive postmarketing experience. Flushing and GI events (abdominal pain, nausea, diarrhea, and vomiting) were among the most commonly experienced AEs with DMF in the 2 pivotal Phase 3 studies [Phillips 2017]. Study 109MS305 showed that DMF had an acceptable safety profile in East Asian participants that was consistent with the profile established in the studies with global participants. Important identified risks for DMF and, hence, DRF include decreases in lymphocyte counts and PML. Data from DRF studies have shown comparability to the DMF safety profile, with no new safety issues identified to date.

In Study ALK8700-A302, which was a 5-week prospective, randomized, blinded control study in participants with RRMS that formally explored differences in GI tolerability between DRF (N = 253) and DMF (N = 251), the duration, incidence, and severity of participant-reported GI symptoms were significantly lower across a multitude of endpoints (including the primary endpoint) in the group of participants treated with DRF compared with the group of participants treated with DMF. The incidence of GI AEs in the DRF group was lower compared with the DMF group (34.8% and 49.0%, respectively), and discontinuations during the Treatment Period due to GI events were also notably less in the DRF group compared with the DMF group (0.8% and 4.8%, respectively) [Naismith 2020]. In Study ALK8700-A301 (N = 1057), interim results showed that DRF is generally well tolerated for up to 96 weeks, and no new safety signals have been identified. The incidence of GI AEs in de novo recruited participants at Week 24 was 27.5%.

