11.1.2. Serious Adverse Event

An SAE is any untoward medical occurrence that at any dose:

- Results in death.
- In the view of the Investigator, places the participant at immediate risk of death (a life-threatening event); however, this does not include an event that, had it occurred in a more severe form, might have caused death.
- Requires inpatient hospitalization or prolongation of existing hospitalization.
- Results in persistent or significant disability/incapacity.

CONFIDENTIAL

The information contained herein may not be used, disclosed, or published without the written consent of Biogen MA Inc.

- Results in a congenital anomaly/birth defect.
- Is a medically important event.

A medically important event is an AE that, in the opinion of the Investigator, may jeopardize the participant or may require intervention to prevent one of the other outcomes listed in the definition above. (Examples of such medical events include allergic bronchospasm requiring intensive treatment in an emergency room or convulsions occurring at home that do not require an inpatient hospitalization.)

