11.3.2. Adverse Events of Special Interest

An AESI is an AE of scientific and medical concern specific to this study, for which ongoing monitoring is required and rapid communication by the Investigator to the Sponsor may be appropriate.

PML and pancreatitis will be considered AESIs. The study site must formally notify the Sponsor within 24 hours of the site staff becoming aware of the AESI.

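### SAP 5.7.3 restricts opportunistic infections to serious events, so the category repeats the serious-infections item and non-serious opportunistic infections other than PML are left out of the special-interest table

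*SAP*

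**What the plan says.** SAP 5.7.3 is a single sentence listing 13 categories of special interest, each with a rule for which events count. The infection-related part reads "Serious and Opportunistic infections (serious events), Infections (serious), Lymphopenia and leucopenia (serious events"). Other items in the sentence carry a wider rule: "PML (all events), Pancreatitis (all events"), then "Pre-malignant conditions (all events), Malignancies (all events"), and cardiac disorders also take all events. Liver injury and GI disorder take serious events and events leading to treatment discontinuation.

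SAP 5.7.2 feeds these categories into one output, "TEAEs of Special Interest by System Organ Class and Preferred Term". It also plans tables of all TEAEs by system organ class and preferred term, and states that "All AEs will be included in the participant-level listings". SAP 5.7.1 asks for all safety summaries by cohort and overall.

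Protocol 3.3 states: "Important identified risks for DMF and, hence, DRF include decreases in lymphocyte counts and PML". Protocol 11.3.2 has a shorter list than the SAP: "PML and pancreatitis will be considered AESIs".

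**The concern.** The title of the first infection category names two things, serious infections and opportunistic infections. The filter attached to it keeps only the serious ones, and the next item already covers those. The word opportunistic then does no work, and one of the two items is redundant.

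Safety and tolerability are the primary objective of both parts of the study, and decreased lymphocyte counts are an important identified risk. Under Protocol 8.1, the lymphocyte criterion for mandatory permanent discontinuation is a count that stays below 0.5 × 10³/µL for more than 6 months, so some participants may be on treatment with low counts. SAP Table 3 follows lymphocytes at three thresholds (0.91, 0.8 and 0.5 × 10⁹/L). A reader who wants to know whether low counts went with unusual infections would turn to the special-interest table. If several non-serious opportunistic infections had occurred, that table would show none of them, and its silence could be read as absence.

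**Working it through.** The point concerns a definition, so the check is mainly one of logic.

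**Step 1. Classify infections and apply the SAP 5.7.3 rules as written.** A is the serious-and-opportunistic item with its serious-events filter, B is the serious-infections item, and P is the PML item (all events).

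| Type of infection | A | B | P | In special-interest table |
|---|---|---|---|---|
| Serious, not opportunistic | yes | yes | no | yes |
| Serious, opportunistic, not PML | yes | yes | no | yes |
| Non-serious, opportunistic, not PML | no | no | no | **no** |
| Non-serious, not opportunistic | no | no | no | no |
| PML, serious | yes | yes | yes | yes |
| PML, non-serious | no | no | yes | yes |

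Columns A and B are identical. If the title of A is read instead as infections that are both serious and opportunistic, A becomes a subset of B and still adds nothing. Compared with a rule of serious infections plus all opportunistic infections, exactly one row is lost, the third. No other item in the sentence is directed at that row.

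**Step 2. Is the filter a general rule?** Of the 13 items, 6 are serious only, 2 are serious or leading to discontinuation (6 + 2 = 8 filtered), and 5 take all events. Seriousness is the commoner rule but not a universal one. Opportunistic infections also lack the discontinuation extension given to liver injury and GI disorder, so a non-serious one that ended treatment would still be outside the category.

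**Step 3. Do the other tables fill the gap?** The complete tables by system organ class and preferred term contain every treatment-emergent event, but no row groups or flags opportunistic infections. The table limited to terms seen in at least 5% of participants does not help with isolated cases: 1/50 = 2% and 2/50 = 4%, both below the cut-off within a cohort.

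**Step 4. How full would a serious-only category be?** SAP 2.3 gives an SAE incidence of 4% over 24 weeks, 50 participants per cohort and an 87% chance of at least one SAE. Check: 1 − 0.96^50 = 0.870, which agrees. The expected number with any SAE is 50 × 0.04 = 2 per cohort over 24 weeks, and infections are only part of these. The serious-infection categories will hold few events, if any.

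**Step 5. Illustration of how often the gap would bite.** The documents give no incidence for non-serious, non-PML opportunistic infection. Assuming a 48-week incidence p, with all n participants followed, P(at least one) = 1 − (1 − p)^n:

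| Assumed p | n = 50 | n = 100 |
|---|---|---|
| 1% | 0.395 | 0.634 |
| 2% | 0.636 | 0.867 |
| 4% | 0.870 | 0.983 |

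These are chances that an event occurs, not that a conclusion changes. The sponsor may also enrol fewer than 50 per cohort, which would lower them.

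**The case against.** The best defence is that nothing goes unreported. All TEAEs are tabulated by system organ class and preferred term, by 4-week interval, by maximum severity and by relationship, and all AEs are listed. In a descriptive single-arm study of about 100 participants, a reader can find each infection. The special-interest table is itself laid out by preferred term, so it contains no category count that would be wrong, and the overlap of two items changes no planned number. This stands as far as data are concerned. It does not supply the missing grouping, because a reader would have to decide term by term which infections are opportunistic.

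Seriousness also offers some protection. Protocol 11.1.2 says "A medically important event is an AE that, in the opinion of the Investigator, may jeopardize the participant", so some opportunistic infections would be classed as serious and kept. That narrows the gap by an unknown amount and leaves it to case-by-case judgement.

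Stronger readings are tempting, and the documents do not support them:

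- A reader might infer that every non-serious opportunistic infection disappears. PML does not, because it is listed with all events.
- A reader might infer a conflict with the protocol. There is none. The protocol's list is PML and pancreatitis only, and the SAP list goes beyond it. How far to extend it is largely the sponsor's choice. AESI wording in the amendment history is superseded and carries no weight here.
- A reader might infer that the documents treat opportunistic infection of any seriousness as the marker of the lymphocyte risk. Protocol 3.3 names lymphocyte decreases and PML and goes no further. The lymphocyte risk is also followed directly, through shift tables, the three thresholds and a listing of participants who need lymphocyte monitoring.

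**Conclusion.** The point holds in limited form. Followed exactly, SAP 5.7.3 defines two infection categories with the same content and leaves non-serious opportunistic infections other than PML out of the special-interest table. What is lost is the ability to see these events as a group. No data are lost, no sample-size or power figure changes, and no protocol commitment is broken.

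The duplication and the gap rest on the text alone and need no assumed rate. The title of the category suggests a drafting slip, but the documents do not settle the intent, and the text needs correcting whether or not the filter was deliberate. How often the gap would matter is unknown, since the 1%, 2% and 4% incidences are assumptions for illustration only. The change is worth making before database lock because safety is the primary objective and the correction is very cheap.

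**What to change.** In SAP 5.7.3, replace the two overlapping items with *Opportunistic infections (all events)* and *Infections (serious events)*.

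State how opportunistic infections are identified, by a MedDRA search or a list of preferred terms tied to the coding version in use and fixed before database lock. SAP 5.7.3 gives no such list, and without one the category cannot be reproduced. The study is open-label, so the list should be drawn up without reference to the events observed.

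In SAP 5.7.2, add to the special-interest table the number and percentage of participants with at least one event in each category, by cohort and overall. The planned table has only system organ class and preferred term rows.

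Cost: one line of SAP text, a term list and one extra table row per category. Data collection, sample size and study conduct are unaffected.

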5.7.4. Clinical Laboratory Parameters

Laboratory assessments include hematology, blood chemistry, and urinalysis with specified parameters in [Appendix C](#).

Descriptive summary statistics for actual values, change from baseline and percent change from baseline will be provided for all quantitative laboratory parameters and presented by cohort and overall.

Mean plots with the corresponding standard error (SE) for selected hematology and chemistry laboratory parameters will be presented for each cohort overlaid on the same plot.

Hematology, blood chemistry, and urinalysis data will be summarized using shift tables. Hematology, chemistry, and continuous/numerical urinalysis laboratory values will be flagged as ‘low,’ ‘normal,’ or ‘high’ relative to the parameter’s normal range. Non-numerical urinalysis laboratory values will be flagged as ‘normal’ (e.g., if result is ‘negative’ or ‘none seen’) or else as abnormal. The number and percentage of participants with shifts from baseline to high or, low, or abnormal status will be presented by cohort. Shift to low includes results from normal to low, high to low, and unknown to low. Shift to high includes results from normal to high, low to high, and unknown to high. Shift to abnormal includes normal to abnormal and unknown to abnormal. For tests with a lower normal range of 0, shift to low is not applicable and will not be displayed.

In each summary, the denominator for the percentage is the number of participants at risk for the shift. The number at risk for the shift to low is the number of participants whose baseline value is not low and who have at least one post-baseline value (based on scheduled and unscheduled visits). The number at risk for the shift to high is the number of participants whose baseline value is not high and who have at least one post-baseline value. The number at risk for the shift to abnormal is the number of participants whose baseline value is not abnormal and who have at least one post-baseline value. A participant will be counted only once for each parameter and each type of shift if there is more than one occurrence for that parameter and that type of shift among post-dose assessments.

In addition, the number and percentage of subjects with values considered potentially clinically significant (PCS) occurring at any post-baseline visit for selected parameters will be summarized using the criteria listed in [Table 3](#).

Table 3: Criteria for Potentially Clinically Significant Laboratory Parameters

Laboratory Parameters	Criteria
Hematology	
White blood cells	$\leq 2.8 \times 10^9/L$
Lymphocytes	$<0.91 \times 10^9/L$ $<0.8 \times 10^9/L$ $<0.5 \times 10^9/L$
Neutrophils	$<1.5 \times 10^9/L$ $\leq 1 \times 10^9/L$
Eosinophils	$>1 \times 10^9/L$
Hemoglobin	$\leq 95g/L$ (female) $\leq 115g/L$ (male)
Platelet count	$\leq 75 \times 10^9/L$ $\geq 700 \times 10^9/L$
Blood Chemistry	
Alanine aminotransferase (ALT)	$>3 \times ULN$ $>5 \times ULN$ $>10 \times ULN$
Aspartate aminotransferase (AST)	$\geq 3 \times ULN$ $>5 \times ULN$ $>10 \times ULN$
ALP	$>3 \times ULN$ $>5 \times ULN$ $>10 \times ULN$
GGT	$\geq 3 \times ULN$
Total bilirubin	$>1.5 \times ULN$ $>2 \times ULN$
Blood urea nitrogen (BUN)	$>10.71 \text{ mmol/L}$
Creatinine	$\geq 176.8 \text{ umol/L}$
Bicarbonate	$<15 \text{ mmol/L}$ $>31 \text{ mmol/L}$
Urinalysis	
Ketones	$\geq +++++$

Protein	$\geq ++$
---------	-----------

For evaluation of potential serious hepatotoxicity, the graphical display of x-y plot of maximum Total bilirubin will be plotted over maximum ALT (alanine aminotransferase) or AST (aspartate aminotransferase), as multiples of ULN in log scale.

Liver function data for participants with potential serious hepatotoxicity that is Total bilirubin $>2 \times \text{ULN}$ and ALT/AST $\geq 3 \times \text{ULN}$ will be provided in the listings.

For each participant with potential serious hepatotoxicity, liver function data will be plotted over time as multiples of ULN in log scale.

All abnormal laboratory data will be included in the participant-level listings. A supporting listing for participants who require additional lymphocyte count monitoring visits, as per the protocol, will also be provided.

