- k. Eligibility related to prior treatment with an investigational drug and/or a commercially available drug for the treatment of MS not listed above within the past 2 years will be determined on a case-by-case basis by the Medical Monitor
- l. Steroids, with the exception of topical or inhaled steroids within 30 days prior to Baseline Visit (Day 1)

Laboratory Values

- 28. Clinically significant abnormal laboratory test values (those that may confound study results or pose risk to the subject through participation in the study), as determined by the Investigator, at Screening or Baseline Visit (Day 1).
- 29. Has any of the following abnormal blood tests at Screening:
 - a. ALT, AST, or GGT $\geq 3 \times \text{ULN}$ or bilirubin $> 2 \times \text{ULN}$.
 - b. TSH level $> 10\%$ of the ULN
 - c. eGFR $\leq 60 \text{ mL/min}/1.73 \text{ m}^2$ (using the Chronic Kidney Disease Epidemiology Collaboration equation) [[Levey 2009](#)]
 - d. Lymphocyte count $< \text{LLN}$
- 30. Has any of the following abnormal urine tests at Screening:
 - a. Beta-2 microglobulin $> 0.3 \mu\text{g/mL}$
 - b. Albumin to creatinine ratio $> 22.6 \text{ mg}/\text{mmol}$

For the parameters listed in Exclusion Criteria 29d and 30, out-of-range values that are clinically not significant, as determined by the Investigator, may be repeated once, and the participant may be enrolled only if the repeated value is within the normal range.

CONFIDENTIAL

The information contained herein may not be used, disclosed, or published without the written consent of Biogen MA Inc.

Other

31. Blood donation (1 unit or more) within 90 days prior to Screening, plasma donation within 1 week prior to Screening, and platelet donation within 6 weeks prior to Screening.
32. History of alcohol or substance abuse within the past year (as determined by the Investigator).
33. Participants who are pregnant or currently breastfeeding and those intending to become pregnant or begin breastfeeding at any point during the study and for 30 days after completing study treatment.
34. Current or prior participation in a clinical trial within 90 days of Screening. Participants who have previously participated in a clinical trial but have not received any IMP treatment within 90 days of Screening will be eligible if the Investigator confirms that the participant meets all other Inclusion and Exclusion criteria and there are no other safety concerns.

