8. DISCONTINUATION OF STUDY TREATMENT AND WITHDRAWAL OF PARTICIPANTS FROM THE STUDY

8.1. Discontinuation of Study Treatment

A participant must permanently discontinue study treatment for any of the following reasons:

- The participant becomes pregnant. Study treatment must be discontinued immediately (Note: Instructions for reporting the pregnancy are provided in Section 11.4.1).
- The participant withdraws consent to continue study treatment.
- The participant experiences an AE that requires permanent discontinuation of study treatment.
- The participant is unwilling or unable to comply with the protocol.
- At the discretion of the Investigator for medical reasons.
- At the discretion of the Sponsor or upon request of a regulatory authority.
- Lymphocyte count $< 0.5 \times 10^3/\mu\text{L}$ persisting for > 6 months. An initial lymphocyte count $< 0.5 \times 10^3/\mu\text{L}$ should be confirmed by repeat testing. If the value remains $< 0.5 \times 10^3/\mu\text{L}$ for > 6 months, the participant must permanently discontinue study treatment. Participants who permanently discontinue the study with a last measured lymphocyte count $< \text{LLN}$ will require additional follow-up to monitor their lymphocyte counts; see [Table 2](#).

The reason for discontinuation of study treatment must be recorded in the CRF.

In addition to the reasons provided above for permanent discontinuation of study treatment, study treatment must be temporarily withheld if any of the following laboratory parameters meet the following threshold limits:

- AST or ALT $> 3 \times \text{ULN}$; confirmed by repeat testing. If the value remains $> 3 \times \text{ULN}$ for ≥ 4 weeks after interruption of study treatment, the participant must permanently discontinue study treatment.
- eGFR $< 60 \text{ mL/min}/1.73 \text{ m}^2$; confirmed by repeat testing as soon as possible. If the eGFR remains $< 60 \text{ mL/min}/1.73 \text{ m}^2$ for ≥ 4 weeks after interruption of study treatment, the participant must permanently discontinue study treatment.
- Urine albumin to urine creatinine ratio $> 22.6 \text{ mg}/\text{mmol}$; confirmed by repeat testing as soon as possible. If the urine albumin to urine creatinine ratio remains $> 22.6 \text{ mg}/\text{mmol}$ for ≥ 4 weeks after interruption of study treatment, the participant must permanently discontinue study treatment.

CONFIDENTIAL

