Appendix C: Laboratory Parameters

Hematology¹	Biochemistry	Urinalysis
Hematocrit	Sodium	Color
Hemoglobin	Potassium	pH
Red blood cell count	Chloride	Specific gravity
Total and differential (absolute) white blood cell count	Bicarbonate	Ketones
Platelets	Glucose	Protein
	Calcium	Glucose
	Uric acid	Bilirubin
	Creatinine ²	Nitrite
	Total protein	Urobilinogen
	Blood urea nitrogen	Occult blood
	Albumin	Microscopic examination of sediment only if urinalysis dipstick results are abnormal
	Total bilirubin	Urine albumin
	ALT	Urine beta-2-microglobulin
	AST	Urine creatinine
	LDH	
	Alkaline phosphatase	
	GGT	
	Creatine phosphokinase	
	Lipid profile: blood cholesterol, high-density lipoprotein, low-density lipoprotein, and triglycerides	
	Serum FSH (to confirm postmenopausal status) ³	
	Vitamin D (1,25-(OH) ²)	
	TSH ³	
	Serum pregnancy ⁴	
	HIV/Hepatitis screen ³	
	TB test ³	

¹ Additional hematology assessments will be collected for participants requiring follow-up for lymphopenia at the time of study completion or ET.

² Serum creatinine will be used to calculate eGFR at each timepoint that a creatinine result is generated.

³ Only at Screening.

⁴ Only at Screening and Safety Follow-Up (Visit 15).

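### SAP Table 3 counts participants at the protocol's hepatic and lymphocyte action limits but not at its two renal withholding limits, and the creatinine row does not substitute for the eGFR limit

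*SAP*

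**What the plan says.** Protocol 8.1 says that "study treatment must be temporarily withheld if any of the following laboratory parameters meet the following threshold limits". It then lists three: AST or ALT > 3 × ULN, eGFR < 60 mL/min/1.73 m², and urine albumin/creatinine ratio > 22.6 mg/mmol. Each must be confirmed by repeat testing. Each leads to permanent discontinuation if it persists for 4 weeks or more after interruption; for the ratio that clause opens "If the urine albumin to urine creatinine ratio remains". A separate rule in the same section covers lymphocytes < 0.5 × 10³/µL persisting for more than 6 months.

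SAP 5.7.4 says that potentially clinically significant (PCS) values "for selected parameters will be summarized using the criteria listed in" Table 3, titled "Criteria for Potentially Clinically Significant Laboratory Parameters". Its renal rows are BUN > 10.71 mmol/L, creatinine ≥ 176.8 µmol/L and dipstick protein ≥ ++.

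SAP Appendix C lists serum creatinine, urine albumin and urine creatinine. eGFR appears in the SAP only in a footnote there: "Serum creatinine will be used to calculate eGFR at each timepoint that a creatinine result is generated". The SAP never mentions the albumin/creatinine ratio. In SAP 5.7.3 the renal event of special interest is "Renal tubular injury (serious events" only), whereas the liver entry also takes in events leading to treatment discontinuation.

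On the eGFR formula, Protocol 6.2 (exclusion criterion 29c) calculates it "using the Chronic Kidney Disease Epidemiology Collaboration equation". Protocol 10.2, Table 5, footnote 2 adds that the participant's latest weight is used. The matching SAP footnote omits the sentence on weight.

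**The concern.** Quantitative and qualitative laboratory change is a primary endpoint in both parts of the study. Table 3 follows the protocol's own action limits for liver enzymes and lymphocytes but drops them for the kidney. Treatment could therefore be interrupted under a renal limit without that crossing being counted in the PCS table.

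Screening excludes eGFR ≤ 60 and a ratio > 22.6 mg/mmol (Protocol 6.2, criteria 29c and 30b), so crossings on treatment would generally be new. With about 50 participants per cohort, each case is 1/50 = 2% of a cohort.

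**Working it through.** The plan states no figure for this comparison, so there is none to reproduce.

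**Step 1. Limits against rows.**

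| Protocol 8.1 limit | SAP Table 3 |
|---|---|
| AST or ALT > 3 × ULN | ALT > 3 × ULN; AST ≥ 3 × ULN |
| Lymphocytes < 0.5 × 10³/µL | < 0.5 × 10⁹/L (the same value) |
| eGFR < 60 mL/min/1.73 m² | No row; nearest are creatinine and BUN |
| Albumin/creatinine ratio > 22.6 mg/mmol | No row; nearest is dipstick protein |

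**Step 2. Does the creatinine row cover the eGFR limit?** The inputs are the 176.8 µmol/L cut (SAP Table 3), the limit of 60 (Protocol 8.1), and ages 18 to 65 in both sexes (Protocol 6.1). The documents name the equation but do not print it. The usual CKD-EPI 2009 form without a race term is assumed:

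eGFR = 141 × min(S/κ, 1)^α × max(S/κ, 1)^−1.209 × 0.993^age × 1.018 (if female)

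Here S is creatinine in mg/dL, κ is 0.7 for women and 0.9 for men, and α does not matter when S > κ. The cut is 176.8/88.4 = 2.00 mg/dL.

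- Man aged 40: 141 × (2.00/0.9)^−1.209 × 0.993^40 = 40.5.
- Woman aged 40: 141 × (2.00/0.7)^−1.209 × 0.993^40 × 1.018 = 30.5.

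Solving the same equation for eGFR = 60 gives the creatinine at which the protocol limit is reached.

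| Sex, age | Creatinine at eGFR 60 (µmol/L) | eGFR at 176.8 µmol/L |
|---|---|---|
| Man, 18 | 145.3 | 47.3 |
| Man, 40 | 127.8 | 40.5 |
| Man, 65 | 110.6 | 34.0 |
| Woman, 18 | 114.7 | 35.5 |
| Woman, 40 | 100.9 | 30.5 |
| Woman, 65 | 87.3 | 25.6 |

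The cut is 176.8/145.3 = 1.2 to 176.8/87.3 = 2.0 times the creatinine that corresponds to the limit. The highest eGFR at the cut is 47.3, so nobody of eligible age with an eGFR of about 48 to 59 meets the creatinine criterion. For women the uncovered band reaches down to about 36 at age 18 and 26 at age 65.

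**Step 3. Other formulas.**

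- CKD-EPI 2021 (assumed coefficients) gives eGFR 27 to 49 at the cut, so the conclusion is the same.
- Because one footnote refers to weight, Cockcroft-Gault was also tried: (140 − age) × weight/(72 × S), × 0.85 if female, in mL/min and not indexed to body surface. At the cut it gives 20 to 58 for 45 to 80 kg, except 68 for an 18-year-old man of 80 kg. At 100 kg it exceeds 60 for men of 18 and 40 (85 and 69) and a woman of 18 (72). For those participants the creatinine row would be reached before the limit of 60.

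**Step 4. The ratio.** A serum creatinine cut says nothing about urinary albumin. Dipstick protein ≥ ++ may catch some cases, but the documents give no conversion, so the share cannot be computed.

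**Step 5. Could another output give the count?**

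- Shift tables (SAP 5.7.4) compare each parameter with its normal range, not with a protocol limit.
- Descriptive statistics show average change, not threshold crossings.
- Listings hold abnormal values without a number and percentage.
- Adverse event tables depend on reporting. Under Protocol 11.1.1 an abnormal result is an adverse event only if it meets the criteria for a serious event, needs corrective therapy, or is judged clinically significant. Meeting a withholding limit is not itself a criterion.

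**The case against.** The strongest reply is that Table 3 is one output among several. Serum creatinine and urine albumin enter shift tables that use scheduled and unscheduled values, and descriptive statistics cover all quantitative parameters. Abnormal values are listed. Non-serious renal events appear in the general TEAE tables, including those for interruption and discontinuation, and reasons for discontinuing treatment are summarised. Protocol 12.5.2 and SAP 5.7.4 promise PCS counts for selected parameters only, and neither document says these must match the withholding limits.

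Most of that stands, and it rules out several stronger readings:

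- A reader might infer that a participant who meets a renal limit appears nowhere as abnormal. The documents do not support this. A raised creatinine or urine albumin can show as a shift to high, and the laboratory's upper limits are not given.
- A reader might infer that everyone between the eGFR limit and the creatinine cut is withheld and unflagged. Withholding needs confirmation on repeat, and BUN or dipstick protein may flag some of them.
- A reader might infer that the SAP ignores eGFR. The Appendix C footnote says it is calculated; what is unclear is whether it counts as a parameter for the summaries. Only the ratio is wholly absent.
- A reader might infer a breach of the protocol. The wording on selected parameters leaves the choice open.

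The formula is also unsettled, and a weight-based one reverses the creatinine result for some younger, heavier participants. None of this supplies the missing count.

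**Conclusion.** The point holds as a gap in a stated criterion. For a primary laboratory endpoint, no planned output gives the number and percentage of participants who crossed the trial's own renal limits, although Table 3 does this for the hepatic and lymphocyte limits.

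The creatinine row is no substitute for the eGFR limit. Under CKD-EPI 2009 it is reached only at an eGFR of about 26 to 47, so the band of about 48 to 59 is never flagged by creatinine. This rests on assumed coefficients and on CKD-EPI being the on-study formula, which the weight footnote puts in doubt. The absence of both rows and of any derivation of the ratio does not depend on the formula.

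The underlying data are collected and partly summarised elsewhere. What is lost is the count, not the data. It should be fixed, but it does not undermine the study.

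**What to change.** 1. Before programming, reconcile Protocol 6.2 (criterion 29c), Protocol 10.2 (Table 5, footnote 2) and SAP Appendix C, so that one eGFR formula is stated for on-study values.
2. Add two rows to SAP Table 3, using the existing Protocol 8.1 limits purely as counting thresholds: eGFR < 60 mL/min/1.73 m² and urine albumin/creatinine ratio > 22.6 mg/mmol. Report each for any post-baseline value and separately for values confirmed on repeat, since a single value does not establish a withholding case.
3. State that unscheduled values count towards these rows. Repeat tests may be unscheduled, and SAP 3.1 keeps unscheduled values out of by-visit summaries.
4. List eGFR and the ratio in Appendix C as derived parameters, with the ratio's derivation from urine albumin and urine creatinine, so that both enter the summaries.

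The cost is two table rows, two derived variables from data already collected, and the formula reconciliation. No clinical rule changes.
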